6.5 TREATMENT DURATION

Patients will receive trial treatment until one of the following criteria applies:

- disease progression,
- unacceptable toxicity or toxicity that results in treatment interruption of >4 weeks,
- patient experiences DLT

- patient decides to withdraw from study, starts a new therapy or is lost to follow up
- discontinuation from the study treatment for any other reason.
- PI or study sponsor discretion

Patients who come off therapy will be followed for survival regardless of cause of treatment discontinuation.”

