6.6 DOSE LIMITING TOXICITIES-PHASE IB COMPONENT

The phase Ib component of the study will consist of 3+3 dose escalation rule with the dose of LEE011 escalating up to 600mg daily to determine the maximum tolerated dose (MTD) that will be used during the phase II component. The dose levels for the phase Ib aspect will be 200 mg, 400 mg, or 600 mg daily.

Only the first cycle of therapy (one cycle equals to one month) will be used to determine dose limiting toxicity (DLT). However, if two total grade 5 adverse events or 2 Grade 4 adverse events (lasting ≥ 7 days); occur at any time while the patient is still receiving study treatment that are either: definitely, probably, or possibly related to either LEE011 or TACE the study will be terminated to enrollment.

Only patients started on the first dose of LEE011 will be included in the evaluation of DLT. If a patient has a DLT that patient will not receive further LEE011. Patients following initial chemoembolization who never receive LEE011 will not be included in the MTD analysis and will be replaced. The patients will be followed for thirty days following the initial chemoembolization for safety assessment. Patients will be enrolled into the next highest drug cohort only after 3 or 6 patients have completed the first cycle of therapy. Once the MTD is determined, patients at the MTD dose will continue with LEE011 and represent the first three patients accrued to the phase II aspect.

Due to observed (TACE related, non DLT) toxicity on cohort 1 specific criteria for cohort 1 has been developed after discussion with the FDA. Cohort 1 has been expanded to 6 patients. Decision for dose escalation will be made using the following criteria:

- No or one DLT: the next three patients will be assigned to next higher dose level (400 mg of LEE011).
- At least two toxicities: the MTD is exceeded and the phase I component of the trial will be stopped with no continuation into the phase II component.

For Cohort 2 and 3 the following traditional 3+3 dose escalation rules will be used:

- If a dose limiting toxicity (DLT) is observed in 1 out of 3 patients at a given dose level, up to 3 additional patients will be enrolled and treated at that dose level.
- If 2 out of 3-6 patients at that dose level have DLTs, the dose will be decreased to the previous dose level, and up to 3 additional patients will be enrolled at that dose level for a total of 6 patients.

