- When up to 3 additional patients are added to a given dose level, if 0-1 of 6 patients has a DLT then the dose will be increased to the next dose level.
- Additional dose levels may be explored per investigator discretion to define the safety profile of the treatment.

The recommended Phase II dose (RP2D) will be the highest cohort level in which one or fewer subjects of 6 develops a first cycle DLT.

The Data and Safety Monitoring Committee as described below will regularly review all serious adverse events and any local adverse events, which are unanticipated problems. The study will utilize the Common Terminology Criteria for Adverse Events (CTCAE) version 4.03 for grading of all adverse events related to treatment.

Table 6.2: Dose-limiting toxicity: phase Ib component

The following will be considered a DLT if they occur within the first cycle of therapy with LEE011 and are determined to be possibly, probably or definitely related to LEE011

Grade 4 neutropenia lasting more than 7 consecutive days
Grade 3 or 4 febrile neutropenia
≥ Grade 3 vomiting ≥ 48 hours despite optimal anti-emetic therapy
≥ Grade 3 diarrhea ≥ 48 hours despite optimal anti-diarrhea therapy
Clinical signs of cardiac disease, such as unstable angina or myocardial infarction, or Troponin ≥ grade 3
Grade 4 serum alkaline phosphatase > 7 days
≥ Grade 3 serum creatinine
≥ Grade 3 adverse event for any non-hematologic toxicity unless otherwise specified as below (excluding alopecia, fatigue < 5 days, laboratory abnormalities that are responsive to oral supplementation or deemed by the investigator to be clinically insignificant).

THROMBOCYTOPENIA	
Toxicity/Grade	Dose Limiting Toxicity and Management Recommendations
Grade 3 ($\geq 25 \times 10^9/L$ - $<50 \times 10^9/L$) without clinically significant bleeding	Dose interruption until recovery to grade ≤ 2 . Re-initiate LEE011 at the same dose level. • If toxicity recurs at grade 3: dose limiting toxicity
Grade 3 ($\geq 25 \times 10^9/L$ - $<50 \times 10^9/L$) with clinically significant bleeding	Dose limiting toxicity
Grade 4 ($<25 \times 10^9/L$)	Dose limiting toxicity

HEPATOTOXICITY (BILIRUBIN, ALT, AST)	
TOTAL BILIRUBIN without ALT/AST increase above baseline value	
Toxicity/Grade	Dose Limiting Toxicity and Management Recommendations
Same grade as baseline or increase from baseline grade 0 to grade 1	Maintain dose level with LFTs monitored every other-week

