Increase from baseline grade 0 or 1 to grade 2 ($1.5-3.0 \times$ ULN) or from baseline grade 2 to grade 3 ($>3.0 -10 \times$ ULN)	Dose interruption of LEE011 If resolved to \leq grade 1 in ≤ 21 days, then maintain dose level If resolved to \leq grade 1 in > 21 days or toxicity recurs, then dose limiting toxicity
Increase from baseline grade 0 or 1 to grade 3 ($>3.0-10$ xULN)	Dose limiting toxicity
Grade 4 ($> 10.0 \times$ ULN)	Dose limiting toxicity

Confounding factors and/or alternative causes for increase of total bilirubin should be excluded before dose interruption/reduction. They include but are not limited to: evidence of obstruction, such as elevated ALP and GGT typical of gall bladder or bile duct disease, hyperbilirubinemia due to the indirect component only (i.e. direct bilirubin component $\leq 1 \times$ ULN) due to hemolysis or Gilbert Syndrome, pharmacologic treatment, viral hepatitis, alcoholic or autoimmune hepatitis, other hepatotoxic drugs.

For patients with Gilbert Syndrome, these dose modifications apply to changes in direct bilirubin only. Bilirubin will be fractionated if elevated.

HEPATOTOXICITY (BILIRUBIN, ALT, AST)

AST or ALT without bilirubin elevation $> 2 \times$ ULN

AST or ALT Toxicity/Grade	Dose Limiting Toxicity and Management Recommendations
Same grade as baseline or increase from baseline grade 0 to grade 1 (confirmed 48 to 72 hrs later)	No dose adjustment required with LFTs monitored per protocol if same grade as baseline or bi-weekly in case of increase from baseline grade 0 to 1
Increase from baseline grade 0 or 1 to grade 2 ($> 3.0 - 5.0 \times$ ULN) or from baseline grade 2 to grade 3 ($> 5.0 - 20.0 \times$ ULN)	Dose interruption of LEE011 If resolved to \leq baseline value in ≤ 21 days, then maintain dose level If resolved to \leq baseline value in > 21 days or toxicity recurs, then dose limiting toxicity
Increase from baseline grade 0 or 1 to grade 3 ($> 5.0 - 20.0 \times$ ULN)	Dose limiting toxicity
Grade 4 ($> 20.0 \times$ ULN)	Dose limiting toxicity

AST or ALT and concurrent Bilirubin	
AST or ALT \geq grade 2 ($> 3 \times$ ULN) in patients with normal values at baseline and total bilirubin $> 2 \times$ ULN or AST or ALT \geq grade 3 ($> 5 \times$ ULN) in patients with grade	Dose limiting toxicity

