7.1 TABLE OF ASSESSMENTS

Treatment Days	Screening Phase ¹		Treatment Phase: Chemoembolization	Treatment Phase: LEE011						Post Treatment Follow-up			Survival Phase
	Day -28 – Day -1	Day -7 – Day -1	7-14 days Following chemoembolization	Cycle 1		Cycle 2		C3	C4+	End of Treatment or Early Withdrawal (Within 15 Days of Last LEE011 Dose)	Safety Follow-Up (Within 30 Days of Last LEE011 Dose)	Efficacy Follow-Up	Survival Follow-Up Every 12 weeks
Visit Assessments				Day 1 ^{2,13}	Day 15	Day 1	Day 15	Day 1	Day 1				
Informed Consent	X												
Demographics	X												
Eligibility Checklist - Inclusion / Exclusion	X												
Med History	X												
Dx and Extent of Cancer (Staging)	X												
Physical Exam		X	X	X	X	X	X	X	X	X	X		
ECOG Status		X	X	X	X	X	X	X	X	X	X		
Height	X												
Weight		X		X	X	X	X	X	X	X	X		
Vital Signs		X	X	X	X	X	X	X	X	X	X		
CBC		X	X	X	X	X	X	X	X	X	X		

Chemistry (CMP)		X	X	X	X	X	X	X	X	X	X			
Cholesterol/Lipid Panel		X		X	X	X	X	X	X	X	X			
PT/INR		X	X	X	X	X	X	X	X	X	X			
Serum Pregnancy Test (WOCBP Only)		X							X	X				
Urinalysis		X								X	X			
Tumor Assessments with RECIST 1.1 ⁵	X			←----- Every 8 weeks ⁵ ----- -----→									X ⁵	
ECHO/MUGA	X													
ECG (12 – Lead)		X ³		X	X	X	X ³	X	X	X	X			
Adverse Events ⁶	X	X		X	X	X		X	X	X	X			
Conmeds ⁶	X	X		X	X	X		X	X	X	X			
Biomarker Tissue Collection (Biopsy) ⁷	X ⁷					X ⁷								
Biomarker Blood Collection ⁸		X		X		X		X	X	X				
LEE011 Study Drug (Oral) ⁹				X		X		X	X					
Patient Dosing Diary for LEE011 ⁹				X		X		X	X					
Chemoembolization (TACE) ¹⁰				X		X		X	X					
Discontinuation ¹¹											X			
Survival Follow-Up ¹²													X	

1. Screening assessments, apart from those listed above, must occur within 28 days of registration as per Table 7.1;
2. Vital Signs, ECOG Performance Status, Physical Exam, ECG, CBC, CMP, PT/INR, Lipid Panel, Serum Pregnancy Test (WOCBP Only), and Urinalysis should be performed within 7 days of the first treatment day (Cycle 1, Day 1). If there are any dose modifications or halting of drug in the phase II aspect, weekly hematology, comprehensive metabolic panels, and PT/INR laboratory investigations will be performed until the grade of adverse event leading to the modification or cessation is stable or a grade reduction occurs. In addition, following each chemoembolization the following will be done every other week for two cycles after each chemoembolization: physical examination, CMP, CBC, and PT/INR.

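### A cycle 1 grade 3 platelet drop that never recovers is scored as a non-DLT, which tilts escalation slightly upward

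*Combined protocol and SAP*

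**What the plan says.** The relevant row of Table 6.2 (section 6.6) covers grade 3 thrombocytopenia without clinically significant bleeding. LEE011 is held until grade 2 or lower and restarted at the same dose. Then: "If toxicity recurs at grade 3: dose limiting toxicity". The row sets no time limit for recovery and has no branch for a count that stays at grade 3. Grade 3 with significant bleeding and grade 4 are immediate DLTs.

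The surrounding rules are these:

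- **Window.** "The following will be considered a DLT if they occur within the first cycle of therapy with LEE011", and only if at least possibly related to LEE011.
- **Who counts.** Section 6.6 limits the DLT evaluation to patients who took a first dose of LEE011. Replacement is confined to the never-dosed: "Patients following initial chemoembolization who never receive LEE011 will not be included in the MTD analysis and will be replaced".
- **Opening the next cohort.** "Patients will be enrolled into the next highest drug cohort only after 3 or 6 patients have completed the first cycle of therapy".
- **Phase II dose.** It is the "highest cohort level in which one or fewer subjects of 6 develops a first cycle DLT".
- **End of treatment.** Section 6.5 stops treatment for "unacceptable toxicity or toxicity that results in treatment interruption of" more than 4 weeks, and lists this separately from experiencing a DLT.
- **Hepatic rows of Table 6.2.** For bilirubin and for AST/ALT, resolution in more than 21 "days or toxicity recurs, then dose limiting toxicity".
- **Blood counts.** Table 7.1 schedules a CBC on days 1 and 15 of cycles 1 and 2. Footnote 2 adds, "every other week for two cycles after each chemoembolization: physical examination, CMP, CBC, and PT/INR". Its weekly tests after a dose hold apply to phase II only.

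**The concern.** The row treats recovery followed by relapse as dose-limiting, but not failure to recover. A patient whose platelets stay at grade 3 cannot be restarted and eventually leaves LEE011, yet adds nothing to the DLT count. That count decides whether the next dose opens and which dose goes to phase II. Leaving out a toxicity that ended treatment can push the decision in one direction only, toward the higher dose. Phase II plans 40 patients, of whom three carry over from phase Ib, so about 37 new patients (40 - 3) would start at the chosen dose.

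Timing adds to the problem. DLTs must fall in the first cycle, but the plan does not say whether onset or completion of the criterion has to fall there.

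**Working it through.** The plan gives no figure of its own on this point. The check is whether another rule captures the event, then timing, then size.

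**1. Does another rule capture it?**

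- The general row of Table 6.2 is for non-hematologic toxicity only.
- The stopping rule in sections 6.6 and 9.4 needs grade 4 or grade 5 events.
- Section 6.5 ends treatment but does not call the event a DLT. For onset on day 15 its limit is reached on about day 15 + 28 = 43, outside the window.
- Table 6-4 governs cycle 2 onward and phase II. It also acts only on recurrence.

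Nothing captures it. The event is outside the DLT list and the patient stays in the evaluation, so the score is a non-DLT.

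**2. Timing.** A drop found at the day 15 CBC reaches 21 days on day 15 + 21 = 36, after the 28-day cycle has ended. The recurrence trigger is tight as well. Days 22-28 are off drug (section 6.3), and the next scheduled count after day 15 is at about day 29 (cycle 2 day 1). Hold, recovery, restart and recurrence can hardly finish by day 28.

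**3. Size.** Let d be the rate of counted DLTs and u the rate of LEE011-related non-recovering events, with patients independent. Both are assumptions: d = 5%, 10%, 20% and u = 1%, 2%. As the plan stands p = d; if non-recovery counted, p = d + u.

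- 3+3 (cohorts 2 and 3): pass = (1-p)^3 + 3p(1-p)^5
- At most 1 DLT in 6 (cohort 1 and the phase II dose rule): pass = (1-p)^6 + 6p(1-p)^5

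Example, 3+3 at d = 10%:

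- As planned: 0.90^3 + 3(0.10)(0.90^5) = 0.7290 + 0.1771 = 0.9061
- Counted, u = 2%: 0.88^3 + 3(0.12)(0.88^5) = 0.6815 + 0.1900 = 0.8715
- Difference: 0.0347 (from unrounded values, as in the table)

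| Rule | d | As planned | Counted, u = 1% | Difference | Counted, u = 2% | Difference |
|---|---|---|---|---|---|---|
| 3+3 | 5% | 0.9734 | 0.9627 | 0.0108 | 0.9505 | 0.0230 |
| 3+3 | 10% | 0.9061 | 0.8892 | 0.0169 | 0.8715 | 0.0347 |
| 3+3 | 20% | 0.7086 | 0.6869 | 0.0217 | 0.6651 | 0.0435 |
| At most 1 in 6 | 5% | 0.9672 | 0.9541 | 0.0132 | 0.9392 | 0.0280 |
| At most 1 in 6 | 10% | 0.8857 | 0.8655 | 0.0202 | 0.8444 | 0.0414 |
| At most 1 in 6 | 20% | 0.6554 | 0.6308 | 0.0246 | 0.6063 | 0.0491 |

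The overstatement runs from about 1 to 5 percentage points.

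**4. Is a low u reasonable?** Section 1.7.4.1 gives a mean effective half-life of 32.6 hours, so 21 days off drug is 21 × 24 / 32.6 = 15.5 half-lives. Drug-related non-recovery should be rare. At u = 1% or 2%, six patients include at least one such case with probability 1 - 0.99^6 = 0.059 or 1 - 0.98^6 = 0.114.

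**The case against.** The strongest reply is that this is a deliberate hematologic policy. Uncomplicated grade 3 neutropenia is never a DLT, anemia has no DLT row, and the grade 2 and 3 QTc rows also act on recurrence. Platelets are already handled more strictly than neutrophils, and the 21-day limit is borrowed from the liver rows. This stands in part: tolerating a grade 3 drop that recovers is a fair clinical choice. But the platelet row itself calls recurrent grade 3 dose-limiting, and it forbids restart without recovery. To count relapse but not a persistent drop that ends treatment is hard to defend within that one row.

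A second reply is attribution. All patients have just had doxorubicin-bead chemoembolization, entry platelets may be as low as 75,000/mm³, and a count still low after 15 half-lives points less clearly to LEE011. Relapse on rechallenge is better evidence. This is fair, but Table 6.2 already requires at least possible relation to LEE011, and the same condition would apply to a non-recovery criterion.

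A third reply is that calling the shift a bias presumes the event ought to count. That is so. The case rests on the view that a LEE011-related toxicity that prevents further dosing is dose-limiting.

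A reader might go further and infer that the plan leaves this patient unclassified, or open to replacement. The documents do not support either. An event outside the closed list is a non-DLT, and only patients who never receive LEE011 are replaced. Completion of the first cycle has no dose-based definition, but section 6.6 equates a cycle with one month, so a calendar reading is natural.

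**Conclusion.** The concern holds. Followed as written, the plan scores a non-recovering, treatment-ending, LEE011-related grade 3 platelet drop in cycle 1 as a tolerated dose. The direction is certain, toward escalation and a higher phase II dose. The size is about 1 to 5 points of pass probability, conditional on assumed non-recovery of 1-2% and counted DLT rates of 5-20%.

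A reader might infer a larger effect from the background rates of grade 3/4 thrombocytopenia: 43% with palbociclib in HCC (section 1.6), and 7 of 67 (10%) with LEE011 600 mg in the first-in-human study (Table 2-1). These are rates of the event, not of failure to recover, and the documents give no figure for the latter.

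The harm is also bounded. Section 16.0 provides real-time review of toxicity and escalation, the planned top dose is the 600 mg recommended from the first-in-human study, and the later dose rules still hold or stop the drug. That study was not specific to HCC, however, and reviewers work better from a written criterion than from a ruling made after the data are seen. Importance is minor to moderate.

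**What to change.** Add two sentences to section 6.6 and Table 6.2:

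1. In the row for grade 3 thrombocytopenia without clinically significant bleeding: failure to recover to grade 2 or lower within 21 days, or permanent discontinuation of LEE011 for the event, is a DLT if at least possibly related to LEE011.
2. For Table 6.2 as a whole: an event with onset in cycle 1 counts as a first-cycle DLT even if its time limit or recurrence falls after day 28, and the cohort decision waits until that patient is classified.

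An optional CBC at the 21-day limit shortens the wait. For onset found on day 15, the decision moves from day 28 to day 36 with that extra count (36 - 28 = 8 days), or to the scheduled cycle 2 day 15 count on day 43 without it (43 - 28 = 15 days). The delay would arise only occasionally. Sample size and the other dose rules are unchanged.

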5.1 INCLUSION CRITERIA

- 5.1.1 Histologically confirmed diagnosis of hepatocellular carcinoma (mixed HCC/cholangiocarcinoma is allowed).
- 5.1.2 **RB positivity as defined by RB expression (score of 0.5 or 1) with concurrent p16in4a loss (score of 0-2);**
- 5.1.3 Patients must have HCC limited to the liver. There must be no definitive

clinical or radiographic evidence of extrahepatic HCC. Portal lymphadenopathy is permitted as lymphadenopathy is commonly associated with cirrhosis unrelated to malignancy;

- 5.1.4 Absence of occlusive main portal vein thrombus, branch venous thrombus is allowed;
- 5.1.5 Patients with locally advanced HCC not eligible for curative therapies;
- 5.1.6 Age \geq 18 years;
- 5.1.7 Child-Pugh Score A or B7;
- 5.1.8 ECOG Performance score of 0-2;
- 5.1.9 Anticipated life expectancy greater than 6 months;
- 5.1.10 Following baseline laboratory values should be met:
 - 5.1.10.1** Total bilirubin \leq 2.0 x ULN or direct bilirubin \leq 1.5 x ULN in patients with well-documented Gilbert's Syndrome;
 - 5.1.10.2** INR \leq 1.7;
 - 5.1.10.3** Hgb \geq 9.0 g/dl;
 - 5.1.10.4** Alkaline Phosphatase, AST, ALT $<$ 5 times ULN;
 - 5.1.10.5** Platelet count \geq 75,000/mm³;
 - 5.1.10.6** Serum creatinine \leq 1.5 mg/dL or creatinine clearance \geq 50 mL/min;
 - 5.1.10.7** Absolute neutrophil \geq 1,500 cells/mm³;
 - 5.1.10.8** Potassium, total calcium (corrected for serum albumin), magnesium, and phosphorus within normal limits for the institution or corrected to within normal limits with supplements;
- 5.1.11 Women of childbearing potential must have a negative pregnancy test;
- 5.1.12 Prior therapy is allowed provided the following are met: at least 4 weeks since prior locoregional therapy including surgical resection, radiotherapy, or

ablation. Provided target lesion has increased in size by 25% or more or the target lesion was not treated with locoregional therapy;

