Grade 3 ANC $< 1.0 \times 10^9/L$ with [a single temperature of $> 38.3^\circ C$ ($101^\circ F$) or a sustained temperature of $\geq 38^\circ C$ ($100.4^\circ F$) for more than one hour]	Dose interruption until improvement of ANC $\geq 1.0 \times 10^9/L$ and no fever. Restart at the next lower dose level. 
 If febrile neutropenia recurs, discontinue LEE011.
Grade 4 Life-threatening consequences; urgent intervention indicated	Discontinue LEE011.
Anemia (Hemoglobin)	
Grade 1 (≥ 10.0 g/dL)	No dose adjustment required.
Grade 2 ($\geq 8.0 - < 10.0$ g/dL)	No dose adjustment required.
Grade 3 (< 8.0 g/dL)	Dose interruption until recovery to grade ≤ 2 . Re-initiate LEE011 at the same dose.

Grade 4 Life-threatening consequences; urgent intervention indicated	Discontinue LEE011.
---	---------------------

**Table 6-5 LEE011 Dose Adjustment and Management Recommendations for
HEPATIC ADVERSE REACTIONS**

HEPATOTOXICITY (BILIRUBIN, ALT, AST)	
TOTAL BILIRUBIN without ALT/AST increase above baseline value	
Grade	Dose Adjustment and Management Recommendations
Same grade as baseline or increase from baseline grade 0 to grade 1	Maintain dose level with LFTs monitored every other-week
Increase from baseline grade 0 or 1 to grade 2 (1.5-3.0 x ULN) or from baseline grade 2 to grade 3 (>3.0 -10 x ULN)	Dose interruption of LEE011 If resolved to \leq grade 1 in \leq 21 days, then maintain dose level If resolved to \leq grade 1 in $>$ 21 days or toxicity recurs, discontinue LEE011

Increase from baseline grade 0 or 1 to grade 3 (>3.0-10 xULN)	Discontinue LEE011
Grade 4 (> 10.0 x ULN)	Discontinue LEE011

Confounding factors and/or alternative causes for increase of total bilirubin should be excluded before dose interruption/reduction. They include but are not limited to: evidence of obstruction, such as elevated ALP and GGT typical of gall bladder or bile duct disease, hyperbilirubinemia due to the indirect component only (i.e. direct bilirubin component ≤ 1 x ULN) due to hemolysis or Gilbert Syndrome, pharmacologic treatment, viral hepatitis, alcoholic or autoimmune hepatitis, other hepatotoxic drugs.
 
For patients with Gilbert Syndrome, these dose modifications apply to changes in direct bilirubin only. Bilirubin will be fractionated if elevated.
	
HEPATOTOXICITY (BILIRUBIN, ALT, AST)	
AST or ALT without bilirubin elevation > 2 x ULN	
AST or ALT Toxicity/Grade	Dose Adjustment and Management Recommendations

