Same grade as baseline or increase from baseline grade 0 to grade 1 (confirmed 48 to 72 hrs later)	No dose adjustment required with LFTs monitored per protocol if same grade as baseline or bi-weekly in case of increase from baseline grade 0 to 1

Increase from baseline grade 0 or 1 to grade 2 ($> 3.0 - 5.0 \times \text{ULN}$) or from baseline grade 2 to grade 3 ($> 5.0 - 20.0 \times \text{ULN}$)
	
Dose interruption of LEE011
 
If resolved to \leq baseline value in ≤ 21 days, then maintain dose level
 
If resolved to \leq baseline value in > 21 days or toxicity recurs, discontinue LEE011

Increase from baseline grade 0 or 1 to grade 3 ($> 5.0 - 20.0 \times \text{ULN}$)
	
Discontinue LEE011

Grade 4 ($> 20.0 \times \text{ULN}$)
	
Discontinue LEE011

AST or ALT and concurrent Bilirubin
	

AST or ALT \geq grade 2 ($> 3 \times \text{ULN}$) in patients with normal values at baseline and total bilirubin $> 2 \times \text{ULN}$ o r AST or ALT \geq grade 3 ($> 5 \times \text{ULN}$) in patients with grade 1 or 2 at baseline, and total bilirubin $> 2 \times \text{ULN}$
	
Discontinue LEE011

Confounding factors and/or alternative causes for increased transaminases should be excluded before dose interruption/reduction. They include but are not limited to: concomitant medications, herbal preparations or dietary supplements, infection, hepato-biliary disorder or obstruction, new or progressive liver metastasis, and alcohol intake.
	

Table 6-6 LEE011 dose modification guidance in case of QT PROLONGATION

The ECG are done based on scheduled assessment as detailed in table 7.1.

QTC	
Grade	Dose Modification
For all grades	
 • Check the quality of the ECG • Perform analysis of serum electrolytes (K+, Ca++, Phos, Mg++). If below the lower limit of normal, interrupt LEE011 administration, correct with supplements or appropriate therapy as soon as possible, and repeat electrolytes until documented as normal • Review concomitant medication usage for the potential to inhibit CYP3A4 and/or to prolong the QT interval • Check compliance with correct dose and administration of LEE011
1 QTc 450-480 ms	No dose adjustment required.

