 - Physical examination
 - Comprehensive metabolic panel
 - Complete blood count without differential
 - Prothrombin time/INR

At this time the decision will be made to initiate LEE011 treatment.

LEE011 ADMINISTRATION WITH CHEMOEMBOLIZATION

Subjects are to be evaluated from toxicity with:

- Physical Examination (PE)
- Comprehensive Metabolic Panel (CMP)
- CBC
- ECG's

LEE011 will be initiated at the earliest of 7 days following embolization chemoembolization provided the following criteria are met:

- Serum bilirubin elevation $< 2.0 \times \text{ULN}$. If serum bilirubin $\geq 2.0 \times \text{ULN}$ then subjects will be assessed weekly and LEE011 will be initiated once bilirubin $< 2.0 \times \text{ULN}$.
- Resolution of Grade < 3 non-hematologic toxicity (other than bilirubin criteria above). If non-hematologic toxicity \geq Grade 3 then subjects will be assessed weekly and LEE011 will be initiated once $<$ Grade 2;
- Hematological toxicity of \leq Grade 2. If hematologic toxicity \geq Grade 3 then subjects will be assessed weekly and LEE011 will be initiated once \leq Grade 2.

If baseline AST, ALT and alkaline phosphate are elevated post chemoembolization decrease to baseline grade is necessary to continue/initiate LEE011;

- ECOG performance status ≤ 2 ;
- Serum AST, ALT, and/or Alkaline Phosphate $< 5 \times \text{ULN}$.

If criteria is not met, subjects will be reevaluated in 5-7 day intervals. If study subjects are unable to meet the above LEE011 starting criteria following initial chemoembolization treatment within 28 days after treatment, they will be removed from the study.

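### The total bilirubin row of Tables 6.2 and 6-5 sets a grade 1 recovery target for baseline grade 2 patients, so a full return to baseline fits neither branch of the rule

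*Combined protocol and SAP*

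**What the plan says.** Protocol section 6.6, Table 6.2, sets the phase Ib DLT rules for total bilirubin without an ALT/AST increase. One row joins two triggers: baseline grade 0 or 1 rising to grade 2, "or from baseline grade 2 to grade 3". The response is to interrupt LEE011. If bilirubin reaches grade 1 or lower within 21 days, the dose level is kept. If it reaches grade 1 or lower only after 21 days, "or toxicity recurs, then dose limiting toxicity".

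Table 6-5 in section 6.7 (phase Ib from cycle 2, and phase II) repeats the row, including "or from baseline grade 2 to grade 3 (>3.0 -10 x ULN", with discontinuation in place of the DLT.

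Four other provisions bear on it:

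- Inclusion criterion 5.1.10.1 caps total bilirubin at "2.0 x ULN or direct bilirubin" limits for Gilbert syndrome.
- The start rules in section 6.12 hold LEE011 while bilirubin is at or above 2.0 x ULN: "then subjects will be assessed weekly and LEE011 will be initiated once bilirubin" is below that value.
- The row headed "AST or ALT without bilirubin elevation" above 2 x ULN has the same two-part trigger, but its recovery target is the patient's baseline value.
- Section 6.5 ends treatment for "unacceptable toxicity or toxicity that results in treatment interruption of >4 weeks".

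**The concern.** A grade 1 target suits a patient who began at grade 0 or 1. It does not suit one who began at grade 2, because that patient can recover completely and still miss it. The row names baseline grade 2 as a trigger and offers a route back to treatment, but the route requires a bilirubin below the level at which the protocol let the patient start.

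Two things are at stake. A patient whose event has fully reversed may lose LEE011 through the interruption limit, whereas the same course in AST or ALT would keep the dose. And in phase Ib the table does not say whether the event is a DLT. Section 6.6 makes that count matter: in cohort 1, two events end phase I with no phase II; in cohorts 2 and 3, two events among 3 to 6 patients send the dose down.

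**Working it through.** The plan gives no figure to reproduce here. The check compares the rule with the bilirubin limits elsewhere in the protocol.

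**Inputs**

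- Grade 2 in the table: 1.5 to 3.0 x ULN; grade 3: above 3.0 to 10 x ULN (Tables 6.2 and 6-5). I take 1.5 x ULN as the top of grade 1.
- Entry limit: 2.0 x ULN (5.1.10.1). LEE011 start limit: below 2.0 x ULN (section 6.12).
- Recovery window: 21 days. Longest interruption: 4 weeks, or 28 days (section 6.5).

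**Step 1: can the case arise?** Yes. A baseline above 1.5 and below 2.0 x ULN is grade 2 and meets both the entry and the start rules.

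**Step 2: follow one patient through the row.** Start at 1.8 x ULN, rise above 3.0, return to 1.8 within 21 days.

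- Keep-dose branch: needs grade 1 or lower. At 1.8 the patient is still grade 2, so it is not met.
- DLT or discontinuation branch: needs late resolution to grade 1 or lower, or recurrence. Neither has happened, so it is not met.
- Result: the interruption continues while bilirubin stays at baseline, and past day 28 section 6.5 ends treatment. In phase Ib no DLT status is assigned.

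**Step 3: how far below baseline must the patient go?** Required fall = 1 - 1.5/baseline. Rise that triggers the row = 3.0/baseline.

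| Baseline (x ULN) | Fall below own baseline needed | Rise needed to pass 3.0 x ULN |
|---|---|---|
| 1.6 | 1 - 1.5/1.6 = 6.2% | 3.0/1.6 = 1.9-fold |
| 1.75 | 1 - 1.5/1.75 = 14.3% | 3.0/1.75 = 1.7-fold |
| 1.9 | 1 - 1.5/1.9 = 21.1% | 3.0/1.9 = 1.6-fold |
| limit 2.0 | 1 - 1.5/2.0 = 25% | 3.0/2.0 = 1.5-fold |

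**Step 4: compare with the AST/ALT row.** The triggers and the 21 days are the same, but the target is the baseline value. A patient back at baseline keeps the dose. In Table 6-5 a late recovery or a recurrence there leads to the same kind of outcome: after 21 "days or toxicity recurs, discontinue LEE011". Only the bilirubin target breaks the pattern.

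**The case against.** The strongest reply is that a stricter bilirubin target is deliberate. Child-Pugh B7 patients may enter, the animal studies name the hepatobiliary system as a target organ, LEE011 inhibits the human bile salt export pump, and section 9.4 is concerned with aggregate severe hepatobiliary toxicity. Nor is the AST/ALT row always more lenient: a baseline grade 0 patient must return to the baseline value there, but only to grade 1 for bilirubin.

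The call for caution stands, and it shapes the fix. As an explanation of the row it does not. Had the protocol meant to bar these patients from resuming, it could have made the event a DLT outright, as it does for baseline grade 0 or 1 rising to grade 3. Instead it offers interruption and resumption. It also lets LEE011 start anywhere below 2.0 x ULN, and another bilirubin row keeps the dose for a patient at baseline grade. No stricter intent is stated.

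That baseline-grade row might be thought to allow resumption. It is a possible reading, but the interruption row sets its own condition and does not refer to it. Two safeguards are real: section 6.7 puts Table 6-5 under the treating physician's judgment, and section 16.0 provides real-time review by the Phase I team and the DSMC. Neither gives a rule for the DLT decision in Table 6.2.

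Stronger readings are tempting. A reader might infer that the reversed event is a DLT, either as non-recovery at day 21 or through the general line on grade 3 non-hematologic toxicity. The text compels neither: the late branch speaks of resolution to grade 1, and the general line yields to toxicities specified separately. A reader might also infer a gap because a 21-day clock can outlast cycle 1. But the lead-in to Table 6.2 counts toxicities that occur in the first cycle, naturally read as onset. The phrasing of the late branch for ordinary non-recovery is a labelling matter.

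**Conclusion.** The point holds as a rule that misfires for a small group. Patients validly treated from a baseline between 1.5 and 2.0 x ULN must end 6% to 21% below that baseline (from 1.6 and 1.9 x ULN; just under 25% at the limit) to keep the dose. A full return to baseline has no outcome in either table. The documents support undefined DLT status and, read literally, loss of LEE011 through the 4-week limit. They do not support saying that the event is a DLT, or that discontinuation is forced in phase II, where discretion applies.

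The reach is narrow. The case needs a 1.5- to 2.0-fold rise, no ALT/AST increase above baseline, other causes excluded, and bilirubin settling back at grade 2. To bear on a DLT it must also fall in cycle 1 and be at least possibly related to LEE011. The documents give no frequency, and I assume none.

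The arithmetic takes baseline as the value at which LEE011 starts. If the screening value is meant, the only difference is that exactly 2.0 x ULN is included. For Gilbert syndrome the rules apply to direct bilirubin, so these figures do not carry over.

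**What to change.** In the total bilirubin row of both tables, separate the two triggers:

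- Baseline grade 0 or 1: leave the grade 1 target as it is.
- Baseline grade 2: if bilirubin is at or below the baseline value, and below 2.0 x ULN, within 21 days, maintain the dose level. If that target is not met by day 21, or toxicity recurs, apply the existing outcome: DLT in Table 6.2, discontinuation in Table 6-5.

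This matches the AST/ALT row and respects the LEE011 start limit. Do not use baseline grade as the target. Grade 2 runs to 3.0 x ULN, so a patient with a baseline of 1.6 who peaks at 3.1 could resume at 2.9 x ULN, well above both baseline and the start limit.

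The cost is a wording change in one row of two tables, with no added tests or patients. The small downside is that a baseline grade 2 patient may resume LEE011 after a grade 3 bilirubin rise that has reversed.
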